In terms of safety, the AEs similar to feeling abnormal, pruritus, and erythema, etc. that were frequently reported in the repeated intravenous dose trial (263-09-001) were selected as notable AEs. Those notable AEs occurred in 1 out of 12 subjects in the OPC-61815 groups and in 3 out of 6 subjects in the placebo group after 2-hour administration. Any causal relationship between the events and the IMP was ruled out except for the pruritus reported in 1 subject of the placebo group. The notable events occurred in 9 out of 12 subjects in the OPC-61815 groups and 2 out of 6 subjects in the placebo group after 5-minute administration. All the events were judged to be related to the IMP. The notable events were reported in 10 out of 11 subjects in the OPC-61815 groups and in 4 out of 6 subjects in the placebo group after 1-minute administration. All the events excluding erythema reported once in 1 subject treated with OPC-61815 were judged to be related to the IMP. All the AEs potentially causally related to the IMP occurred during or immediately after intravenous administration. Most of those events resolved without treatment within 10 minutes after the start of IMP administration. Because there were no clinically significant changes from baseline in plasma histamine concentration, the cause of the notable AEs is unclear.

Please refer to the IB for more detailed information.

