1.3 Known and Potential Risks and Benefits

OPC-61815 has never been administered to patients with heart failure. No deaths or other serious adverse events (SAEs) were reported in the phase 1 trials in healthy adult male subjects (263-08-001, 263-09-001, and 263-10-005). Feeling abnormal, feeling hot, pruritus, erythema, hyperhidrosis, nausea, epigastric discomfort, and dyspnea were the significant AEs reported following bolus intravenous administration (over 1 or 5 minutes) of OPC-61815 in Trial 263-09-001 or 263-10-005. Significant AEs were defined as those similar to feeling abnormal, pruritus, and erythema, etc. that were reported frequently in the repeated intravenous dose trial (263-09-001).

As noted earlier, OPC-61815 has not previously been administered to patients with heart failure. Nevertheless, OPC-61815 should have similar benefits to tolvaptan because, when the phosphate ester of OPC-61815 is hydrolyzed by alkali and acid phosphatase in the body, tolvaptan forms and acts as an aquaretic agent. Tolvaptan has been shown to relieve weight increase and other signs commonly observed in patients with cardiac edema (jugular venous distension, hepatomegaly, and lower limb edema).

In a clinical trial in patients with cardiac edema, the following AEs were frequently reported among 437 patients given tolvaptan (in \geq 2% incidence among tolvaptan-treated patients and at a higher frequency than in placebo-treated patients): ventricular tachycardia, constipation, dry mouth, diarrhoea, vomiting, thirst, blood urea increased, blood uric acid increased, blood creatinine increased, blood potassium increased, blood sodium increased, blood glucose increased, blood urine present, platelet count decreased, dehydration, hyperkalaemia, dizziness, pollakiuria, renal impairment, and epistaxis.

Please refer to the IB for more detailed information.

2 Trial Rationale and Objectives

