13	exceeding 3 times the upper limit of normal) Subjects who are unable to seems thirst or who have difficulty with fluid inteles
14	Subjects who are unable to sense thirst or who have difficulty with fluid intake Females who are breast-feeding and/or who have a positive pregnancy test result prior to receiving
17	investigational medicinal product (IMP)
15	Sexually active males or women of childbearing potential (WOCBP) who do not agree to practice
	birth control or remain abstinent during the trial and for 30 days after the last administration of IMP
16	Subjects treated with another IMP within 30 days prior to the screening examination
17	Subjects who are otherwise judged to be ineligible by the investigator or subinvestigator

Nonchildbearing potential is defined as male and female subjects who are surgically sterile (ie, male subjects who have undergone bilateral orchidectomy and female subjects who have undergone bilateral oophorectomy and/or hysterectomy) and female subjects who have been postmenopausal for at least 12 consecutive months.

Subjects must agree to restrictions as described in Section 4.

[Rationale	e for exclusion criteria]
1	This criterion is set because subjects must be able to swallow the tolvaptan tablet (control) and
	because acute onset or worsening of symptoms can make trial continuation difficult.
2	This criterion is set because OPC-61815 is intended for patients with volume overload due to
	CHF.
3	This criterion is set to avoid potential influence on efficacy and safety evaluation in the trial.
4	This criterion is set because excessive diuretic therapy is undesirable.
5, 6	These criteria are set for safety reasons.
7	This criterion is set for safety reasons and because such subjects are considered ineligible for
	participation in the trial.
8	This criterion is set for safety reasons.
9	This criterion is set because efficacy evaluation will be difficult in such subjects.
10	This criterion is set because diuresis may decrease blood pressure.
11 to 13	These criteria are set for safety reasons.
14 to 17	These criteria are set for general safety and ethical considerations.

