3.7 Trial Procedures

Table 3.7-1 summarizes the scheduled observations/tests and assessments.

Confidential - Proprietary Information

Table 3.7-1 Schedule of Observations/Tests and Assessments

Time Point	Screen	ning	Rı	ın-in Per	iod			Trea	tment Pe	riod		Follow-up
Item	Day-7 to -4	Day-4	Day-3	Day-2	Day-1	Dayl	Day2	Day3	Day4	Day5/ End of treatment	End-of-trial/At discontinuation (day after final administration)	Day 12 to 15/ 7 to 10 days after final administration
Informed consent												
Consent for DNA storage (optional)			0									
Subject demographics												
Inclusion/Exclusion criteria					•							
Confirmation of use of concomitant medications/ therapies	<											>
Subject registration,	_					•=	•					
randomization ^a												
Hospitalization		<									\rightarrow	
IMP administration							•					
Treatment compliance						←				\longrightarrow		
Use of diuretics (dose fixed)										-		
Plasma drug concentration (See Table 3.7-2)						•=	•	•	•	•	•	
Pharmacodynamics		ļ					!	l			ļ	Į.
Serum sodium and potassium						•=						
concentrations	_					•						-
Serum osmolality, biomarkers ^c						•					•	
Daily urine volume, daily fluid intake, urine sodium/potassium concentrations, urine osmolality			-	→ <	><	> ←	*	*	> <	*	\rightarrow	
Efficacy	1	ı	_		_		T _			I -		ı
Body weight	-		•	•	•	•	•	•	•	•	•	
Congestive symptoms ^g										•		
Chest X-ray ^h				■J								
NYHA Classification				■ ^j								
Safety												
AEs	<											
Clinical laboratory test						•					•	
Physical examination	•					•						
Vital signs d			•	•	•	•	•	•	•	•	•	
12-Lead ECG ^e				■ ^j								
Pregnancy test f	•											
Pharmacogenomics												
DNA Storage ⁱ						0						

- •, Mandatory (before breakfast and IMP administration [before breakfast on the day on which IMP administration is not scheduled]); •, Mandatory (at the specified time point)
- Optional (only applicable to the trial sites that have agreed to collect samples for DNA storage in advance. Samples for DNA storage will only be collected from subjects who have given written consent to DNA storage.)

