3.7.1.4 Treatment Period (Day 1)

(1) Before IMP Administration (Before Breakfast)

- Plasma drug concentration (within 2 hours before IMP administration)
- Serum sodium concentration, serum potassium concentration, serum osmolality, and biomarkers
- Clinical laboratory tests and vital signs
- Body weight
- Blood sampling for DNA storage (The subject may or may not agree to DNA storage. The subject's consent to DNA storage will be obtained before blood sampling.)

(2) After Tests/Blood Sampling and After Breakfast

The subject will be asked to void his/her bladder immediately after breakfast to start pooling of urine and measurement of fluid intake for the following measurements:

- Daily urine volume, daily fluid intake, and daily fluid balance
- Daily urine sodium excretion and daily urine potassium excretion
- Urine osmolality

(3) IMP Administration

The investigator or subinvestigator will administer the IMP to the subject after verifying that the subject meets the inclusion criteria and does not fall under any of the exclusion criteria. The investigator or subinvestigator subsequently will record IMP administration in the IWRS.

(4) Administration of Diuretics

(5) Tests and Assessments

The investigator or subinvestigator will perform the tests described below.

Table 3.7.1.4-1 Tests on Day 1, Their Scheduled Time Points, and Blood Sampling Time Points After IMP Administration							
Sampi							
Item	Time Point	Time Window					
Plasma drug concentration	1 hour after start of IMP	Within 5 minutes after end					
	administration	of IMP administration					
	1.5 hours after start of IMP	Specified time point ± 5					
	administration	minutes					
	2 hours after start of IMP	Specified time point ± 5					
	administration	minutes					
	4 hours after start of IMP	Specified time point ± 20					
	administration	minutes					
	6 hours after start of IMP	Specified time point ± 30					
	administration	minutes					
	12 hours after start of IMP	Specified time point ± 1 hour					
	administration						
Serum sodium concentration,	4 to 6 hours after start of IMP						
serum potassium concentration	administration						
	8 to 12 hours after start of IMP						
	administration						
12-lead ECG	1 to 2 hours after start of IMP						
	administration						
Physical examination	When appropriate on Day 1						
Congestive symptoms	When appropriate on Day 1						
Confirmation of use of	When appropriate on Day 1						
concomitant drugs and therapies	-						

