3.7.1.5 Treatment Period (Day 2)

(1) Before IMP Administration (Before Breakfast)

- Plasma drug concentration (24 hours after start of IMP administration on Day 1)
- Serum sodium concentration and serum potassium concentration
- Vital signs
- Body weight

(2) After Tests/Blood Sampling and After Breakfast

The subject will be asked to void his/her bladder immediately after breakfast to start pooling of urine and measurement of fluid intake for the following measurements:

• Daily urine volume, daily fluid intake, and daily fluid balance

- Daily urine sodium excretion and daily urine potassium excretion
- Urine osmolality
- (3) IMP Administration
- (4) Administration of Diuretics
- (5) When Appropriate on Day 2
 - Physical examination
 - Congestive symptoms
 - Confirmation of use of concomitant drugs and therapies
 - Treatment compliance
 - AEs

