3.7.1.9 Post-treatment Follow-up Period (7 to 10 days after final administration)

The investigator or subinvestigator will perform the following tests or examinations between 7 and 10 days after final IMP administration. The tests/examinations may be performed on an outpatient basis if the subject has been discharged.

- Serum sodium concentration and serum potassium concentration
- Clinical laboratory tests, physical examination, and vital signs
- Body weight and congestive symptoms
- Urine pregnancy test (only in female subjects of childbearing potential)
- Confirmation of use of concomitant drugs and therapies
- AEs

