9.4 Vital Sign Data

Descriptive statistics will be calculated for vital signs together with the changes from baseline at each time point and after final administration.

9.5 **Electrocardiogram Data**

Descriptive statistics of each 12-lead electrocardiogram (ECG) parameter and the changes from baseline in each parameter at each time point and after final administration will be calculated.

The number and percentage of subjects who have a QTc interval (QTcB, QTcF) of “> 450 msec”, “> 480 msec”, and “> 500 msec” at at least one postdose time point or after final administration will be calculated. In addition, the number and percentage of subjects who show a change of “> 30 msec” and “> 60 msec” in QTc interval from baseline at at least one postdose time point or after final administration will be calculated. The numbers and percentages of subjects will also be calculated at baseline and each postdose time point in the same manner. “Normal” and “abnormal” assessments at each postdose time point and after final administration compared with baseline will be summarized in a shift table. “Normal” and “abnormal” assessments by the trial site (investigator or subinvestigator) will be used instead of the assessments by the central ECG analysis laboratory.

10 **Pharmacokinetic Analyses**

This section describes the pharmacokinetics of primary and secondary endpoints.

- 1) Endpoints
 - a) Primary Endpoint :
 - C_{max} and AUC_{24h} of plasma tolvaptan on Day 1 of treatment period
 - b) Secondary Endpoints:
 - i) Plasma concentrations of OPC-61815, tolvaptan, DM-4103 and DM-4107
 - ii) Plasma pharmacokinetic parameters of OPC-61815, tolvaptan, DM-4103 and DM-4107
 - Day 1 of treatment period: C_{max}^a , AUC_{24h}^a , AUC_t , AUC_{∞} , t_{max} , λ_z , $AUC_ \%Extrap$, t_{last} , $t_{1/2,z}$, CL^b , CL/BW^b , V_z^b , V_z/BW^b , CL/F^c , $CL/F/BW^c$
 - Day 1, Day 2, Day 3, Day 4, and Day 5 of treatment period: C_{24h}^d
 - Day 5 of treatment period: $R_{5,ac}(C_{24h})$

^aExcluding tolvaptan

^bCalculated only for OPC-61815 after administration of OPC-61815 injection

^cCalculated only for tolvaptan after administration of tolvaptan 15-mg tablet

^dFor calculation of descriptive statistics, C_{24h} will be handled as plasma concentrations.

iii) Ratio of the AUC of metabolite to that of OPC-61815^e

Day 1 of treatment period: AUC_{∞} , AUC_{24h} , and AUC_t

^eCalculated only for the OPC-61815 injection groups

2) Handling of Data

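### From Day 1 to Day 6 every scheduled blood pressure reading is taken before breakfast, so a transient fall after dosing cannot appear in the vital-sign summaries

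*Protocol*

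**What the plan says.** Blood pressure, pulse rate and body temperature are a named safety endpoint (Protocol 3.5.3), and comparing safety with the tablet is part of the secondary objective (Protocol 2.4).

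**Timing of vital signs**
- Day 1 (Protocol 3.7.1.4): "Clinical laboratory tests and vital signs" stands in block (1), before dosing and before breakfast.
- Days 2 to 5 (Protocol 3.7.1.5 to 3.7.1.7): the same block, headed on Day 2 "1) Before IMP Administration (Before Breakfast)".
- Day 6 (Protocol 3.7.1.8): before breakfast; no dose is given that day.
- The legend of Table 3.7-1 gives the slot as "Mandatory (before breakfast and IMP administration [before breakfast on the day on which IMP administration is not scheduled". The text copy does not separate the table symbols cleanly, but the day-by-day sections say the same without them.
- Follow-up, 7 to 10 days after the last dose (Protocol 3.7.1.9): "Clinical laboratory tests, physical examination, and vital signs", with no time of day. Screening gives no time of day either.

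**Scheduled after dosing.** Table 3.7.1.4-1 (Day 1) lists drug concentrations, serum sodium and potassium, a 12-lead ECG at 1 to 2 h, physical examination, congestive symptoms, concomitant drugs, compliance and adverse events. It does not list vital signs. Day 3 adds an ECG at 1 to 2 h (Protocol 3.7.1.6 (5)).

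**Analysis.** SAP 3.4 builds summaries from scheduled visits, leaves out unscheduled ones, and sets the vital-sign baseline at the Day 1 pre-dose reading. SAP 9.4: "Descriptive statistics will be calculated for vital signs together with the changes from baseline at each time point and after final administration".

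**Why blood pressure is of interest.** The reason given for excluding supine systolic pressure below 90 mmHg is "This criterion is set because diuresis may decrease blood pressure" (Protocol 3.4.4). Protocol 1.3 adds: "OPC-61815 has never been administered to patients with heart failure".

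**The concern.** The protocol expects that diuresis can lower blood pressure, and this is the drug's first use in heart failure. Drug level and urine output change most in the hours after dosing, yet the blood pressure endpoint is read only in the morning. ECG and electrolytes do have post-dose time points; blood pressure is the exception, and no reason is given.

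At stake is a secondary safety comparison in a trial meant to inform the phase 3 dose (Protocol 7.1). If a higher dose caused a short-lived fall, the vital-sign tables would not show it in the injection groups or in the tablet group. A reading taken for care outside the schedule would not enter those tables either.

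**Working it through.** The plan states no figure to reproduce here. The check compares the schedule with the times of interest.

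**Step 1. Lag between a dose and the next blood pressure reading.** No window is given for vital signs. The plasma sample in the same morning block has a window of 22 to 24 h after the previous dose (Table 3.7-2), and I assume the cuff reading shares it.

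The 12-hour statement does not depend on that assumption. From Day 2 each dose starts within 20 minutes either side of the Day 1 clock time (Protocol 3.2.1). Consecutive doses are therefore at least 24 h − (20 + 20) min = 23 h 20 min apart. A Day 2 to 5 reading within 12 h of the previous dose would have to precede that day's own dose by more than 23 h 20 min − 12 h = 11 h 20 min. That is not credible for a reading before breakfast when the dose follows breakfast. Day 6 has no dose, but its block carries the same 22 to 24 h sample.

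**Step 2. Count scheduled blood pressure readings in each post-dose window.**

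| Window after start of dosing | Source | Readings |
|---|---|---|
| Infusion, 0–1 h (55 to 65 min allowed) | Protocol 3.2.1 | 0 |
| 1–2 h, around intravenous tolvaptan t_max of 1.5 h (simulated, healthy adults) | Protocol 2.3, Table 2.3-5 | 0 |
| 2–4 h, around tablet t_max of 2 h (Protocol) or 4 h (SAP) | Protocol 2.3; SAP 10 | 0 |
| 0.75–2.75 h, peak urine rate (0.75–1.25 h after bolus, 2.75 h with 2-hour infusion) | Protocol 2.3 | 0 |
| First 12 h after any dose | Step 1 | 0 |
| Next morning, about 22–24 h | Assumed from Table 3.7-2 | 5 (Days 2 to 6) |

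**Step 3. What each kind of change would reach.**
- *Transient fall, recovered by morning:* no scheduled reading meets it, and SAP 3.4 excludes an unscheduled one. It cannot appear in the SAP 9.4 summaries. SAP Appendix 2 lists vital signs by subject, so an extra reading entered in the CRF might still be listed, but it would not be compared between groups.
- *Sustained or cumulative fall:* the five readings on Days 2 to 6 are compared with the Day 1 pre-dose value, so it can appear.
- *Heart rate:* the ECG at 1–2 h on Days 1 and 3 gives a centrally calculated heart rate (Protocol 3.7.4.4), summarised by time point (SAP 9.5).
- *Hypotension that is noticed:* reportable as an adverse event (Protocol 5.2), outside the vital-sign endpoint.

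**Step 4. Precision of added readings.** The documents give no standard deviation for blood pressure change. Assume 12 to 15 mmHg with 10 per group. The 95% half-width for a difference between two groups is t(0.975, 18 df) × SD × √(2/10):
- SD 12: 2.101 × 12 × 0.447 = 11.3 mmHg
- SD 15: 2.101 × 15 × 0.447 = 14.1 mmHg

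**The case against.** The strongest reply is that this is a design choice in a pharmacokinetic trial. The documents agree with one another, the primary endpoint is Day 1 exposure, and vital signs are only described. Subjects are inpatients, the investigator or subinvestigator gives each dose, and physical examination and adverse event assessment are listed for Day 1 after dosing. Administration follows a separate written procedure (Protocol 3.2.1) that is not among the documents, so bedside monitoring can be neither confirmed nor excluded. Groups of about 10 would separate doses poorly, as Step 4 shows.

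Most of this stands and limits the weight of the point, but it does not close the gap. Whatever is done at the bedside, nothing in the protocol or SAP brings a post-dose blood pressure into the analysis. Protocol 3.7.4.3 lists physical examination by body system and treats blood pressure as a separate item.

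A reader might infer more than the documents support:
- *No fall after dosing could appear in any group, or changes will be near zero.* The Day 2 to 6 readings can show a sustained or cumulative fall, and nothing in the documents predicts near-zero changes.
- *Pulse is not captured after dosing.* The ECG supplies heart rate on two days.
- *Little drug remains by morning, so the readings are free of effect.* The stated mechanism is diuresis, and plasma drug does not measure volume loss. Protocol 3.2.1 reports that earlier patients' body weight stayed lower than on placebo throughout treatment.
- *Phase 1 already showed a circulatory effect.* Protocol 1.2 does say "All the AEs potentially causally related to the IMP occurred during or immediately after intravenous administration", but the events named in 1.2 and 1.3 are symptoms and skin reactions. None is a blood pressure event, and similar events also occurred on placebo.

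**Conclusion.** The point holds in limited form. None of the scheduled blood pressure readings falls within the first 12 h after any of the five doses. A transient fall that recovers by the next morning therefore cannot appear in the vital-sign summaries, in any of the five groups. The schedule and the SAP rule on unscheduled values are enough to establish this; only the 22 to 24 h lag is an assumption. How often such a fall would occur, and how large it would be, cannot be judged from the documents. The primary analysis is unaffected. This is a cheap improvement to a secondary safety comparison, not an error that undermines the trial.

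**What to change.** In Table 3.7-1, Table 3.7.1.4-1 and Protocol 3.7.1.6 (5), add supine blood pressure with pulse at three existing contacts: the 1–2 h ECG on Day 1, the 1–2 h ECG on Day 3, and the 4–6 h sodium and potassium draw on Day 1. The rest rule in Protocol 3.7.4.3 would apply. Enter them in the CRF as scheduled time points, so that SAP 3.4 does not drop them and SAP 9.4, which already covers each time point, summarises them against the Day 1 pre-dose baseline.

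The cost is three extra cuff readings per subject and the matching CRF fields, with no extra visits, staff or blood, and no change to dosing or stopping rules. There are two limits. The readings cover the end of infusion and later, not the infusion itself, and may miss a peak between 2 and 4 h. At about 10 per group they should be presented as descriptive.

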3.7.1.5 Treatment Period (Day 2)

(1) Before IMP Administration (Before Breakfast)

- Plasma drug concentration (24 hours after start of IMP administration on Day 1)
- Serum sodium concentration and serum potassium concentration
- Vital signs
- Body weight

(2) After Tests/Blood Sampling and After Breakfast

The subject will be asked to void his/her bladder immediately after breakfast to start pooling of urine and measurement of fluid intake for the following measurements:

• Daily urine volume, daily fluid intake, and daily fluid balance

- Daily urine sodium excretion and daily urine potassium excretion
- Urine osmolality
- (3) IMP Administration
- (4) Administration of Diuretics
- (5) When Appropriate on Day 2
 - Physical examination
 - Congestive symptoms
 - Confirmation of use of concomitant drugs and therapies
 - Treatment compliance
 - AEs

3.7.1.6 Treatment Period (Day 3)

- (1) Before IMP Administration (Before Breakfast)
 - Plasma drug concentration (24 hours after start of IMP administration on Day 2)
 - Serum sodium concentration and serum potassium concentration
 - Vital signs
 - Body weight

(2) After Tests/Blood Sampling and After Breakfast

The subject will be asked to void his/her bladder immediately after breakfast to start pooling of urine and measurement of fluid intake for the following measurements:

- Daily urine volume, daily fluid intake, and daily fluid balance
- Daily urine sodium excretion and daily urine potassium excretion
- Urine osmolality
- (3) IMP Administration
- (4) Administration of Diuretics
- (5) One to 2 Hours after IMP Administration
 - 12-lead ECG
- (6) When Appropriate on Day 3
 - Physical examination
 - Congestive symptoms
 - Concomitant drugs and therapies
 - Treatment compliance

• AEs

